The Pan-London Perioperative Audit and Research Network (PLAN): [name], [name], [name], [name], [name], [name], [name], [name], [name], [name], [name], [name], [name], [name], [name], [name], [name], [name], [name], [name], [name], [name], [name], [name], [name].

Web: www.uk-plan.net

Statistician:

[name] and [name]

DREAMY Research Team:

Designated collaborators, Clinical Trials Assistants and/or Research Nurses for the DREAMY study. Led by [name].

3 Protocol synopsis

| | |
|--------------------------------------|--|
| Official title: | Direct reporting of awareness in maternity patients: a prospective evaluation of accidental awareness under general anaesthesia in obstetric surgery patients |
| Brief title /Acronym: | DREAMY |
| Sponsor reference number: | 16.0063 |
| Public database trial ID: | TBC |
| Research Question | What is the incidence of AAGA (accidental awareness under general anaesthesia) using a Brice questionnaire in obstetric anaesthesia in the UK? |
| Study design | Observational non-interventional |
| Eligibility criteria: | Inclusion criteria: 
 1. Female adults (≥ 18 years) of $\geq 24/40$ gestation 2. Receiving general anaesthesia (de novo or regional anaesthesia converted to GA) for surgery with an obstetric indication |
| | Exclusion criteria: 
 1. Patients too unwell or confused to be able to complete the questionnaire 2. Patient refusal 3. General anaesthesia for non-obstetric indication (e.g. colorectal or orthopaedic surgery in a pregnant patient) 4. Surgery ≥ 48 hours post-partum 5. Unable to communicate verbally/in writing in English language |
| Anticipated start date | February 2017 |
| Anticipated end date | February 2019 |
| Target number of participants | 2250 |
| Primary aim | Establish the incidence of AAGA using a Brice questionnaire in obstetric anaesthesia in the UK |
| Secondary aim(s) | Investigate the experience and psychological implications of Brice positive AAGA episodes in obstetric patients. This will include 12 month outcome reporting, using structured follow up and the Post-Traumatic Stress Disorder Checklist (PCL-5), alongside case review of the surgical, anaesthetic and patient factors that make obstetric patients more likely to report AAGA than the non-obstetric population. |
| Sources of funding | OAA/NIAA Large Project Grant 2016 for £29,757 |
| Sponsor | St George's NHS Hospitals Foundation Trust |
| Contact name | Sponsor representative: [name] Email: [contact] [contact] [contact] Chief Investigator: [name] Email: [contact] [contact] |

4 Background

Accidental awareness during general anaesthesia (AAGA) can be defined as the unintended experience and explicit recall of sensory perceptions during surgery [Joint commission 2014]. As one of the few direct “complications” of anaesthesia, AAGA has received increasing attention, most notably by the recent 5th National Audit Project (NAP5) [NAP5]. AAGA is considered important to patients and anaesthetists, ranked as the second most important complication of anaesthesia by both groups [Macario 1999, Macario 1999]. Patient experiences of AAGA vary considerably; ranging from neutral with no adverse consequence [Sebel 2004], to intense distress with subsequently post-traumatic stress disorder [Aceto 2013]. NAP5 identified 41% of AAGA cases as being associated with moderate to severe longer-term harm, which was more common in patients experiencing pain and/or paralysis, with 51% reporting moderate to severe harm versus 25% of those reporting only auditory or tactile sensations.

One of the headline results from NAP5 was the disproportionately high incidence of AAGA for obstetric patients undergoing LSCS (~1:670 versus ~1:19,000 overall). General anaesthetics for obstetric patients recurrently typify many of the risk factors for AAGA identified by NAP5 and previous studies: rapid sequence induction, neuromuscular blockade, difficult airway management, obesity and frequent performance out-of-hours by non-consultant grade anaesthetists. This combination of factors is particular, if not unique, to obstetric anaesthetic practice and mandates classification of the subspecialty as high risk for AAGA. Furthermore, in n = 3/14 (21%) of cases of obstetric AAGA identified by NAP5, new significant psychological morbidity was reported. In one case the patient indicated a decision to litigate, which may also indicate further psychological harm.

The James Lind Alliance Anaesthesia and Perioperative Care Priority Setting Partnership identified the following question as being one of the top ten most important research topics in anaesthesia: “What long-term harm may result from anaesthesia, particularly following repeated anaesthetics?” [JLA PSP]. As the highest risk subgroup for one of the most important causes of harm following anaesthesia, obstetric anaesthetic practice warrants further research into AAGA. More explicitly, NAP5 set specific research implications for obstetrics, suggesting that further research was needed to “...define the incidence of AAGA as identified by the Brice questionnaire” [Research Implication 16.6, NAP5] and “to explore whether factors make obstetric patients more likely to report episodes of AAGA than the non-obstetric population” [Research Implication 16.7, NAP5].

The Brice questionnaire [Brice 1970] has been used as a common standard in awareness research. Although minor variations have been applied [Avidan 2009], all retain the same five questions on recall of any events between induction of anaesthesia and emergence. Importantly, direct and systematic questioning is applied when using Brice questionnaires, which contrast with spontaneously patient reporting of AAGA in NAP5. This difference in methodology may partly account for the apparent divergence between the proportion of AAGA consistently reported in the overall surgical population with Brice questioning (~1:660) versus that by NAP5 (~1:19,000 overall). Although few studies have compared methods of AAGA testing, the Brice questionnaire is known to detect more cases of AAGA than unstructured direct questioning [Mashour 2013, Mashour 2009], and timing/repetition of Brice questioning may also influence the output [Mashour 2013, Sandin 2007, Davidson 2005, Leslie 2007]. These limitations, coupled with the debated gulf between incidence of AAGA established by Brice responses alone versus spontaneously reported incidence, mean that Brice has been regarded by some as not the “gold standard” methodology it is frequently implied to be [Cook 2015]. However, where Brice is uniquely important is as a common tool for comparison and as a screening method to identify a subpopulation that may be at need of further investigation.

Brice questionnaires have been applied only once before in obstetric patients [Paech 2009]. This observation study was primarily designed to investigate difficult airways in obstetric patients receiving a GA, but Brice questionnaires were also offered up to day two following surgery. A total 763 of 1095 obstetric patients were provided Brice questionnaires, of whom five cases were “Brice positive”, yielding an estimate of AAGA incidence of ~1:152. Of these, two were classed as “definite” and three as possible awareness. This preliminary study indicates that Brice positivity may indeed be much higher than it is in the general population. However, the lack of follow up beyond 48 hours, the wide confidence intervals and the fact that AAGA was not the study’s primary outcome make these results somewhat difficult to interpret.

The most complete approach to investigating AAGA would be to screen all eligible individuals with a standardised tool, then rigorously assess each potential report with further investigation, before reaching a consensus classification of the event against pre-established definitions of AAGA. This is exactly the methodology to be adopted by our DREAMY study, using Brice questionnaire as the screening tool, but adding structured follow up, where appropriate, to elucidate the nature of the possible AAGA experience and its consequences. By taking this approach the research team aim to produce the most comprehensive analysis of AAGA in obstetric patients to date.

5 Research Question

The DREAMY study aims to fulfil research implications 16.6 and 16.7 from the National Audit Project 5 (NAP5) Report, in relation to AAGA in the obstetric population. These implications are to “...define the incidence of AAGA as identified by the Brice questionnaire” [Research Implication 16.6, NAP5] and “to explore whether factors make obstetric patients more likely to report episodes of AAGA than the non-obstetric population” [Research Implication 16.7, NAP5].

There are three competing research hypotheses: that the incidence of Brice positivity in obstetrics is similar to that of the general population (~1:660), similar to Paech’s [Paech 2009] already reported incidence (~1:152) or that the ratio between “Brice positive” and spontaneous reporting is maintained with the general population (~1:19).

5.1 Primary Aim

The primary aim is to determine, using direct questioning with a Brice questionnaire, the proportion of women who report AAGA following general anaesthesia for obstetric indication surgery in the UK.

5.2 Secondary Aim(s)

A secondary aim is to investigate the experience and psychological implications of AAGA in obstetric patients. This will include 12 month outcome reporting, using structured follow up and the Post-Traumatic Stress Disorder Checklist (PCL-5); alongside case review of the surgical, anaesthetic and patient factors that make obstetric patients more likely to report AAGA than the non-obstetric population.

6 Study design

DREAMY is a prospective, observational, multi-centre cohort study, with recruitment planned for 12 months. Written consent will be obtained from all participants. Any NHS hospital with maternity services and obstetric anaesthesia personnel will be eligible to participate. The study has been designed to maximise feasibility by complementing nationally recommended anaesthetic follow up practice [OAA/AAGBI 2013] for obstetric patients following surgery.

6.1 Methods

Patients receiving GA for obstetric indication surgery will be eligible to participate in the DREAMY study. Participants will be screened for AAGA using three repetitions of the Brice questionnaire, before assessment with structured investigation of their AAGA experience and its psychological consequences. No clinical interventions will form part of the study protocol, but local clinical teams will be encouraged to offer AAGA patient care in accordance with the NAP5 AAGA Support Pathway [NAP5 Anaesthesia Awareness Support Pathway]. Analysis and classification of events will follow pre-established AAGA definitions.

[figure not shown]

Figure 1. Schematic diagram of study design

6.2 Data collection procedures

There are three stages to participant data collection:

1. In hospital: Screening for AAGA with modified Brice questionnaires and collection of baseline anaesthetic episode data
2. After hospital: telephone follow up with repetition of the Brice questions at 30 days after the index GA
3. Conditional follow up, dependent upon Brice response: structured interview schedules for participants reporting Suspected AAGA, extended follow up of AAGA patients after 3 months, identification of PTSD risk factors and PTSD symptom screening for 12 months.

Initial AAGA screening will occur at three time intervals following a participant's index GA: 0-24 hours, 24-48 hours and 30 days. 0-24h and 24-48h follow up will consist of a modified Brice questionnaire [Brice 1970, Avidan 2009], including categorical and free text responses (see [Appendix 2](#) for the modified Brice questions). Day 30 (+/- 5 days) follow up will be conducted via telephone (or via email, at participant request) using the same Brice question format and response options. Data collection following discharge of the patient from the local hospital site will be coordinated and conducted by the DREAMY Research Team, rather than local site investigators. Modification to the above timeline for Brice questionnaire administration will only be made in exceptions when patients are unable to provide responses at the pre-specified time points and in agreement with the local PI/CI.

Any patient with Brice questionnaire responses indicating possible recall of events during the anaesthetic episode (hereafter termed "Brice positive") will be provided with a specific structured interview schedule or questionnaire to further delineate the characteristics and psychological response to their experience (adapted from the BAG-RECALL trial [Avidan 2011]). Further repetitions of the Brice questionnaire will not be required after a participant has been declared "Brice positive". See [section 9.2](#) for further detail on Brice questionnaire response classification.

Suspected AAGA face-to-face or telephone structured interview schedules will be organised and led by the DREAMY Research Team and provided at the earliest available opportunity. See [Appendix 4](#) for the structured follow up questions for patients with Suspected AAGA.

The default follow up methodology for encounters led by the DREAMY Research Team will be telephone structured interview schedules. At the start of the study equivalent written/email questionnaire forms of the interview questions will be provided to maximise follow up data collection. Alignment of responses between different data collection formats will be maximised by using interview schedules structured identically to paper questionnaires and presenting both with simple, equivalent contextual information. During interim analysis if a response format (i.e. telephone, face-to-face or written) is found to be infrequently selected by participants, then this choice may later be removed to further maximise data concordance.

"Brice positive" respondents will receive targeted questions on risk factors for post-natal PTSD ([Appendix 6](#)) during 30 day follow up and be offered the PCL-5 PTSD checklist ([Appendix 5](#)) at 30 days, 3, 6, 9 and 12 months following the index anaesthetic episode. The questions and checklist will be administered by telephone (or via email, at participant request) by the DREAMY Research Team.

An extended questionnaire for "Brice positive" participants will also be undertaken during the 3 month PTSD follow up episode ([Appendix 7](#)). This questionnaire is designed to explore the nature of local clinical follow received by patients and how the AAGA episode has impacted on attitudes towards future anaesthetics and post-natal experience.

Anaesthetic episode data collection will be conducted retrospectively by the anaesthetic Local Investigators from patient notes and anaesthetic records after each participant has provided written consent for study involvement. Data collected on the anaesthetic episode is detailed in [Appendix 3](#) and includes: age of patient, parity, procedure, urgency of surgery/LSCS, ASA status, booking BMI, anaesthesia start/finish time, induction agents (and doses), de novo or conversion to GA, indication for GA, rapid sequence induction, maintenance agent, nitrous oxide use, MAC, (lowest, highest, estimated median), primary airway device, difficult intubation, grade of laryngoscopy, local/regional anaesthesia, neuromuscular blockade, nerve stimulator use, reversal use, depth of anaesthesia monitor use, most senior anaesthetist present, location of extubation, post op destination, estimated blood loss.

1. 0h = Time of GA for obstetric indication surgery.
2. 0-24h following index GA = Written consent obtained. Modified Brice questionnaire (repetition 1). Data collected for the anaesthetic episode.
3. 24-48h following index GA = Modified Brice questionnaire (repetition 2).
4. Day 30 (+/- 5 days) from index GA = Modified Brice questionnaire (repetition 3).

If a participant reports possible recall of events during the anaesthetic episode (“Brice positive”):

1. Participants will be offered a further Suspected AAGA structured interview schedule or questionnaire (adapted from the BAG-RECALL trial [Avidan 2011]). Questionnaires are available in paper form for distribution to inpatients by Local Investigators. Interviews can be conducted via telephone or face-to-face. Suspected AAGA follow up will be made at the earliest available opportunity and in a format of the participant’s preference.
2. “Brice positive” notification will be shared between the local clinical teams and the DREAMY Research Team.
3. Local clinical care teams will be encouraged to offer care in accordance with the NAP5 awareness support pathway [NAP5 Anaesthesia Awareness Support Pathway].
4. Post-Traumatic Stress Disorder (PTSD) Checklist (PCL-5) at day 30, 3, 6, 9 and 12 months.
5. Post-natal PTSD risk factor questions at day 30.
6. AAGA Extended follow up at 3 months, exploring patient attitudes and post-AAGA clinical support.

An initial minimum sample of the first 300 Brice -ve patients completing day 30 follow up will also receive:

1. PCL-5 checklist and targeted questions on risk factors for post-natal PTSD at day 30. This provides a comparator group for PTSD incidence and baseline characteristics in the post-natal period for AAGA vs. non-AAGA patients.

Figure 2. Summary of in-hospital, telephone and conditional DREAMY data collection procedures

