9.2 Modified Brice Questionnaire

Screening for AAGA is being assessed in this study using the Brice Questionnaire, which has been adapted from the original published form [Brice 1970] in accordance with common usage [Avidan 2011]. Questions used in the modified Brice questionnaire are available in [Appendix 2](#). Initial screening will be done by local investigator teams, who will be invited to contact the CI or DREAMY Research Team members with any queries regarding Brice response classification. All Local Investigators will be provided with training to ensure that responses are assessed in a consistent manner. In assessing whether a response should be assigned as “Brice positive”, investigators will be instructed to focus on memories of events that could occur only in the operating room during the anaesthetic and surgical periods. Participant reports of memories during the period between "going to sleep" and "waking up" will be taken as “Yes” answers to any of Q3, Q4 or Q5 or “Awareness” to Q6. Any such responses, indicating possible AAGA, require the Local Investigator to follow the Suspected AAGA follow up protocol (see [section 9.3](#)). If an investigator is in any doubt about whether the Brice Questionnaire responses constitute a possible AAGA event, then the responses should be discussed with the local PI and/or CI.

Final classification of Brice responses will be performed by the same expert panel responsible for making final AAGA classification decisions.

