10.2 Data collection tool

Case Report Forms have been designed by the CI and approved by the protocol authors. All data will be entered legibly in black ink with a ball-point pen. If the Investigator makes an error, it will be crossed through with a single line in such a way to ensure that the original entry can still be read. The correct entry will then be clearly inserted. The amendment will be initialled and dated by the person making the correction immediately. Overwriting or use of correction fluid will not be permitted.

It is the Investigator's responsibility to ensure the accuracy of all data entered and recorded in the CRFs. The Staff Delegation of Responsibilities Log JREOLOG0004 will identify all study personnel responsible for data collection, entry, handling and managing the database.

Data collection tools are used along the following schedule:

| Timing | Data collection | Format | Responsible |
|---|---|---|--|
| 0-24h | Modified Brice Questionnaire (repetition 1) | Written questionnaire | Local investigators |
| 24-48h | Modified Brice Questionnaire (repetition 2) | Written questionnaire | Local investigators |
| Any time (ideally 0-48h) | Anaesthetic Episode data collection | Written CRF | Local investigators |
| Any time "Brice +ve" responses identified | Suspected AAGA Questionnaire | Telephone structured interview schedule (or face-to-face structured interview schedule or written questionnaire) | DREAMY Research Team (if identified at Day 30) or Local Investigators (if inpatient) |
| Day 30 (+/- 5 days) | Modified Brice Questionnaire (repetition 3) | Telephone structured interview schedule (or written questionnaire) | DREAMY Research Team |

| | | | |
|---------------------|---|---|----------------------|
| Day 30 (+/- 5 days) | If "Brice positive": PCL-5 Post-Traumatic Stress Checklist Post-natal PTSD risk factors questions | Telephone structured interview schedule (or written questionnaire) | DREAMY Research Team |
| 3 months | If "Brice positive": PCL-5 Post-Traumatic Stress Checklist AAGA Extended follow up | Telephone structured interview schedule (or written questionnaire) | DREAMY Research Team |
| 6 months | If "Brice positive": PCL-5 Post-Traumatic Stress Checklist | Telephone structured interview schedule (or written questionnaire) | DREAMY Research Team |
| 9 months | If "Brice positive": PCL-5 Post-Traumatic Stress Checklist | Telephone structured interview schedule (or written questionnaire) | DREAMY Research Team |

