12.1.2 Secondary endpoints

The secondary endpoints are:

1. Descriptors of anaesthetic, surgical and patient factors associated with AAGA
2. 3, 6, 9 and 12 month results of the Post-Traumatic Stress Disorder Checklist (PCL-5), for patients with confirmed AAGA. This will be compared with PTSD incidence in the initial cohort of non-AAGA participants.
3. Qualitative description of the experience of AAGA undergone by obstetric patients.

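### Appendix 3 data may be abstracted by staff who know the Brice result, because the protocol leaves the timing open and does not mask the abstractor

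*Protocol*

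**What the plan says.** **Who abstracts, and how.** Section 6.2: "Anaesthetic episode data collection will be conducted retrospectively by the anaesthetic Local Investigators from patient notes and anaesthetic records after each participant has provided" consent in writing. Section 8 places consent before the questionnaire.

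**When.** Two places differ. The Figure 2 summary in section 6.2 has one step: "0-24h following index GA = Written consent obtained. Modified Brice questionnaire (repetition 1). Data collected for the anaesthetic episode". The schedule table in section 10.2 reads: "Any time (ideally 0-48h) | Anaesthetic Episode data collection | Written CRF | Local investigators".

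**Who handles the Brice answers.** The same table assigns the first questionnaire to the same role: "0-24h | Modified Brice Questionnaire (repetition 1) | Written questionnaire | Local investigators". The second in-hospital repetition is assigned likewise. Section 9.2 adds: "Initial screening will be done by local investigator teams". The day-30 repetition belongs to the central research team (section 6.2), and an expert panel makes the final classification (section 9.2).

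**What the data are for.** The first secondary endpoint (section 12.1.2) is "Descriptors of anaesthetic, surgical and patient factors associated with AAGA". Section 12.2.2 plans subgroups by type and urgency of procedure, by de novo GA or conversion, and by propofol or thiopental. Section 12.2.3 plans association tests and, if events suffice, a multivariable model giving odds ratios.

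No section masks the abstractor to Brice status, asks for a different person, or requires the form to be finished before the answers are read.

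**The concern.** A site that follows the protocol can complete Appendix 3 after it knows that a woman is Brice positive. By then section 9.3 has the case under discussion with the PI or CI and calls for urgent upload. Brice-negative women get no such attention. Section 4 also names in advance the risk factors that the investigators expect, difficult airway management among them.

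Several Appendix 3 items need judgement or a search of the record: lowest, highest and estimated median MAC, difficult intubation with its free text, whether a supraglottic device was used because of difficulty, indication for GA, and urgency. If these are recorded more fully for positive women, an association can appear where none exists, and no later analysis fully removes it. At stake are the first secondary endpoint, the urgency subgroup and any multivariable model.

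**Working it through.** The protocol states no figure on this point. The check is a comparison of texts, followed by an illustration of size.

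**1. Order of events.** Consent comes first (sections 6.2 and 8), and abstraction may start only after it. Figure 2 lists abstraction after the first Brice questionnaire within the same 0-24h step. Section 10.2 sets no closing time. Both tasks sit with Local Investigators. So abstraction with knowledge of a positive in-hospital result is permitted. It is neither required nor prevented.

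**2. Day-30 positives.** These women are identified by the central team. A form completed within 48h is protected. A late form is not, because Figure 2 has positive status shared with the local clinical team.

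**3. Illustration of size.** All inputs here are assumptions, not protocol figures: true odds ratio 1; factor truly present in 10% of women; a proportion *s1* of true instances recorded where the abstractor knows of a positive result, and *s0* otherwise; status known at abstraction for a share *f* of cases.

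Recorded prevalence in cases: d = 0.10 × [f·s1 + (1 − f)·s0]. In non-cases: c = 0.10 × s0. Recorded OR = [d/(1 − d)] / [c/(1 − c)].

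| s1 v s0 | f = 1 | f = 0.5 | f = 0.25 |
|---|---|---|---|
| 95% v 70% | 1.39 | 1.19 | 1.10 |
| 100% v 60% | 1.74 | 1.36 | 1.18 |

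First cell: odds in cases are 0.095 ÷ 0.905 = 0.1050, odds in non-cases are 0.070 ÷ 0.930 = 0.0753, and their ratio is 1.39. Second row, f = 1: odds in cases are 0.10 ÷ 0.90 = 0.1111, odds in non-cases are 0.06 ÷ 0.94 = 0.0638, and their ratio is 1.74. First row, f = 0.5: d = 0.10 × 0.825 = 0.0825, so odds in cases are 0.0899, odds in non-cases are again 0.0753, and their ratio is 1.19.

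**4. A different assumed mechanism.** Suppose 30% exposure is recorded in non-cases, and a share *u* of 10% to 30% of unexposed cases is recorded as exposed where status is known. Then d = 0.30 + 0.70·u·f, and the OR runs from 1.09 (u = 0.1, f = 0.25) to 2.43 (u = 0.3, f = 1). If abstraction is masked or completed first, the OR is 1.0. The result depends on the inputs chosen, so none of these values is an estimate.

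**5. Sensitivity to single records.** Section 12.2.2 expects about 15 positives under its second hypothesis. Against an assumed 10% in non-cases (odds 1/9), 2 exposed of 15 gives (2/13)/(1/9) = 1.38, and 3 of 15 gives (3/12)/(1/9) = 2.25. One record read differently moves the estimate that far.

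**6. Against sampling error.** The standard error of the log OR is the square root of the summed reciprocals of the four cell counts. With 15 events of 2,250 and 10% exposure, the counts are 1.5 exposed and 13.5 unexposed cases, with 223.5 exposed and 2011.5 unexposed non-cases. The standard error is 0.864, so the 95% limits are the OR multiplied and divided by exp(1.96 × 0.864) ≈ 5.4. With 118 events the counts are 11.8 exposed and 106.2 unexposed cases, with 213.2 exposed and 1918.8 unexposed non-cases. The standard error is 0.315, a factor of about 1.85.

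**The case against.** The strongest reply is that the protocol intends early abstraction from records that already exist. Figure 2 says 0-24h, the data-collection stages in section 6.2 place these data in the hospital stay, and the section 10.2 window carries an ideal of 48h. Most Appendix 3 fields are tick-boxes or doses that leave little to interpretation. The expert panel, not the site, settles the outcome. The model is conditional on enough events, and sampling error exceeds the illustrated bias in the section 3 table even with 118 events.

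Much of this stands. It limits the fields and women affected, and it bars any claim about actual size. It does not close the gap. Figure 2's own step lists abstraction after the first questionnaire. The panel protects classification of the outcome, not recording of exposure. Wide intervals do not correct a systematic error.

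A reader might go further and infer that the same anaesthetists score the Brice answers and then abstract the data knowing who reported awareness. The documents do not support that. The overlap is of role: section 9.2 speaks of local investigator teams, and no text says that one individual does both. Knowledge of status is possible, not stated. Nor are all the planned subgroups compromised: induction agent and de novo or converted GA are factual entries, and of the named subgroups only urgency rests on a field open to judgement.

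**Conclusion.** The concern holds as a permitted risk. One role screens the in-hospital Brice answers and abstracts Appendix 3, the two statements of timing differ, and nothing masks the abstractor. Differential recording is possible in the MAC values, difficult intubation, the reason for a supraglottic device, indication for GA and urgency. It could affect the first secondary endpoint, the urgency subgroup and any multivariable model. The primary proportion does not use these fields.

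The size is unknown. An odds ratio of about 1.4 to 1.7 from a true value of 1 is an illustration. It assumes 10% prevalence, recording of 95% v 70% or 100% v 60%, and status known for every case. It shrinks to between 1.10 and 1.36 if status is known for a quarter to a half of cases. The point is worth correcting because the remedy is cheap and the bias cannot be fully undone once the data are recorded.

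**What to change.** - Reconcile the Figure 2 summary (section 6.2) with the section 10.2 schedule. State that the paper Appendix 3 form is completed after consent and before the Brice answers are read or scored, for example while the woman fills in the written questionnaire. Alternatively, an existing team member who has not seen the answers completes it, where one is available.
- State that this order must not delay action on a positive response.
- Add to the paper form the date and time of abstraction and whether Brice status was known. REDCap timestamps will not serve, because section 10.4 has data written on paper first, so they show entry rather than abstraction.
- Repeat the factor analyses restricted to forms completed without knowledge of Brice status.

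The cost is a change in the order of two existing forms, two added items and one sensitivity analysis. No compulsory second abstractor is needed, nor a hard lock on the form. The downside is that some forms will still be late and must be flagged, and with few events the restricted analysis will be imprecise.
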